Appendix A

3d	• Diabetes mellitus	
Measured any time prior to and including day of drug initiation in any diagnosis position and any care setting
 
Type 1, Type 2 diabetes mellitus ICD-9 diagnosis: 250.x1, 250.x3, 250.x0, 250.x2 ICD-10 diagnosis: E10.x, E11.x
	
Paterno, Elisabetta et al. "Cardiovascular outcomes associated with canagliflozin versus other non-glipizide antidiabetic drugs: population based cohort study." BMJ 2018;360:k119 http://dx.doi.org/10.1136/bmj.k119
 
Paterno, Elisabetta et al. "Empagliflozin and the Risk of Heart Failure Hospitalization in Routine Clinical Care: A First Analysis from the Empagliflozin Comparative Effectiveness and Safety (EMPRISE) Study." Circulation. 2019 Apr 8. doi: 10.1161/CIRCULATIONAHA.118.039177

3e	• Hypertension requiring pharmacological treatment	
Measured 180 days to 3650 days prior to and including day of drug initiation in any diagnosis position and inpatient or outpatient care setting
 
Hypertension ICD-9 diagnosis: 401.x – 405.x ICD-10 diagnosis: I10.x – I13.x, I15.x
 
Plus following medication use on the same day: (Hypertension Medications sheet) ACE/ARB/beta-blocker/Calcium channel blockers/thiazides/loop diuretics/other diuretics/other hypertensive medications
	
Paterno, Elisabetta et al. "Cardiovascular outcomes associated with canagliflozin versus other non-glipizide antidiabetic drugs: population based cohort study." BMJ 2018;360:k119 http://dx.doi.org/10.1136/bmj.k119
 
Paterno, Elisabetta et al. "Empagliflozin and the Risk of Heart Failure Hospitalization in Routine Clinical Care: A First Analysis from the Empagliflozin Comparative Effectiveness and Safety (EMPRISE) Study." Circulation. 2019 Apr 8. doi: 10.1161/CIRCULATIONAHA.118.039177

4	Women of childbearing potential (WOCBP) must be using an adequate method of contraception to avoid pregnancy throughout the treatment period of the study or for 2 weeks after the last dose of study medication, whichever is longer, in such a manner that the risk of pregnancy is minimized.	N/A - Incorporated in the exclusion criteria.	
5	WOCBP must have a negative serum or urine pregnancy test (minimum sensitivity 25 IU/L or equivalent units of HCG) within 48 hours prior to the start of investigational product.	N/A - Incorporated in the exclusion criteria.	
6	All subjects must provide signed written informed consent.	N/A	
EXCLUSION CRITERIA			
1	Atrial fibrillation or flutter due to reversible causes (e.g. thyrotoxicosis, pericarditis)	N/A	
2	Clinically significant (moderate or severe) mitral stenosis	
Measured 180 days prior to and including day of drug initiation in any diagnosis position and inpatient or outpatient care setting
 
Mitral stenosis ICD-9 diagnosis: 396.0x, 396.1x, 394, 746.5 ICD-10 diagnosis: I34.2x, I05.1x, I05.2x
	
3	Increased bleeding risk that is believed to be a contraindication to oral anticoagulation (e.g. previous intracranial hemorrhage)	
Measured 180 days prior to and including day of drug initiation in any diagnosis position and inpatient care setting
 
Intracranial hemorrhage ICD-9 diagnosis: 430.x, 431.x, 432.x
	
4	Conditions other than atrial fibrillation that require chronic anticoagulation (e.g. prosthetic mechanical heart valve)	
Measured 180 days prior to and including day of drug initiation in any diagnosis position and inpatient or outpatient care setting
 
ICD-9 diagnosis: V43.3x ICD-10 diagnosis: Z95.2x
 
CPT procedure codes: (TAVR with prosthetic valve) 33361, 33362, 33363, 33364, 33365, 33366, 33367, 33368, 33369, 33477, 0483T, 0484T, 0569T, 0570T
	
5	Persistent, uncontrolled hypertension (systolic BP > 180 mm Hg, or diastolic BP > 100 mm Hg)	
Measured 180 days prior to and including day of drug initiation in any diagnosis position and inpatient or ED care setting
 
Malignant hypertension ICD-9 diagnosis: 401.0x
 
Hypertensive urgency/Hypertensive crisis ICD-10 diagnosis: I16.xx
	
6	Active infective endocarditis	
Measured 180 days prior to and including day of drug initiation in any diagnosis position and inpatient or outpatient care setting
 
Endocarditis ICD-9 diagnosis: 421.xx ICD-10 diagnosis: I33.xx
	
7	Planned major surgery	N/A	
8	Planned atrial fibrillation or flutter ablation procedure	N/A	
9	Use of an unapproved , investigational drug or device within the past 30 days	N/A	
10	Required treatment with aspirin >165 mg/day	N/A	
11	Simultaneous treatment with both aspirin and a thienopyridine (e.g., clopidogrel, ticlopidine)	
Measured 14 days prior to and including day of drug initiation
 
Days supply overlap of >7 days of: 1) Prescription for any dose of Aspirin (Note: Unable to capture over the counter use.) AND 2) Prescription for any dose of Clopidogrel/Ticlopidine/prasugrel
	
12	Severe comorbid condition with life expectancy of ≤ 1 year	
Measured 180 days prior to and including day of drug initiation
 
CCI ≥ 10
	

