5.2.1 Eligible cohort entry dates

Market availability of apixaban in the U.S. started on December 28, 2012.

- For Medicare: January 01, 2013- December 31, 2017 (end of available data)
- For Marketscan: January 01, 2013- December 31, 2018 (end of available data)
- For Optum: January 01, 2013- December 31, 2019 (end of available data)

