5.3 Flowchart of the study cohort assembly

For apixaban vs. warfarin

	Optum		Truven		Medicare	
	Less Excluded Patients	Remaining Patients	Less Excluded Patients	Remaining Patients	Less Excluded Patients	Remaining Patients
All patients		75,894,642		200,203,908		6,886,908

Patients with claim for apixaban or warfarin	-74,955,393	939,249	-199,377,918	825,990	-2,374,503	4,512,405
Excluded due to insufficient enrollment	-87,255	851,994	-66,419	759,571	-1,340,098	3,172,307
Excluded due to prior use of warfarin	-390,759	461,235	-426,157	333,414	-1,802,129	1,370,178
Excluded due to prior use of apixaban 5mg	-250,816	210,419	-139,097	194,317	-545,919	824,259
Excluded because patient qualified in >1 exposure category	-21	210,398	-5	194,312	-51	824,208
Excluded based on missing Age	-563	209,835	0	194,312	-136	824,072
Excluded based on missing Gender	0	209,835	0	194,312	0	824,072
Inclusion 3 - Age >= 18	-82	209,753	-187	194,125	-68	824,004
Inclusion #2- Afib (Inpatient, principal) 7 days prior OR Afib or flutter (any setting, any position) 2 diagnoses separated by 14 to 351 days, measured 365 days prior to drug initiation	-86406	123,347	-96150	97,975	-275611	548,393
Inclusion #3- One or more of the 5 risk factor(s) for stroke	-2636	120,711	-2941	95,034	-5239	543,154
Excluded based on Exclusion #2- Mitral Stenosis (any position, any setting)	-320	120,391	-127	94,907	-626	542,528
Excluded based on Exclusion #3 - intracranial hemorrhage	-503	119,888	-309	94,598	-1823	540,705
Excluded based on Exclusion #4 - Prosthetic heart valve	-1916	117,972	-1004	93,594	-8562	532,143
Excluded based on Exclusion #5 - Uncontrolled hypertension	-701	117,271	-218	93,376	-1753	530,390
Excluded based on Exclusion #6 - Active infective endocarditis	-83	117,188	-43	93,333	-456	529,934
Excluded based on Exclusion #11 - Aspirin and Thienopyridine days supply overlap >7 days, measured 14 days prior to drug initiation	-10	117,178	-24	93,309	**	**
Excluded based on Exclusion #12- CCI (180 days)>=10	-5059	112,119	-1788	91,521	-6685	523,239
Excluded based on Exclusion #13- Active alcohol or drug abuse	-1381	110,738	-563	90,958	-5143	518,096
Excluded based on Exclusion #14 - Ischemic stroke (w and w/o mention of cerebral infarction)- 7 days prior	-1178	109,560	-558	90,400	-5741	512,355
Excluded based on Exclusion #15 - Severe renal impairment	-9885	99,675	-5151	85,249	-50219	462,136
Excluded based on Exclusion #17 - Thrombocytopenia	-411	99,264	-290	84,959	-2040	460,096

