Appendix A

#	ARISTOTLE trial definitions	Implementation in routine care	References/Rationale	Color coding
	Trial details- Primary approval, Unintended S with label change		
Please see the following Google Drive for further details or any missing information: https://drive.google.com/open?id=1WD618wrvwYfEaXrlTcuKVConb6b-gU
	Criteria
	EXPOSURE vs. COMPARISON		
ICD-10 codes are not listed in this document because of excel cell size limitations and excessive number of ICD-10 codes. Full ICD-10 code lists will be available in the above Google Drive Folder (link above). ICD-9 to ICD-10 code conversions were completed using a SAS macro that implements forward/backward mapping based on the CMS ICD-9 to ICD-10 mapping: https://www.ncbi.nlm.nih.gov/pmc/articles/PMC3074733/
	Adequate mapping in claims
	apixaban (at a dose of 5 mg twice daily) versus warfarin (target international normalized ratio, 2.0 to 3.0)	Apixaban 5mg vs warfarin		Intermediate mapping in claims
	PRIMARY OUTCOME			Poor mapping or cannot be measured in claims

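### Exclusion 2: the printed ICD-10 list for mitral stenosis does not match the ICD-9 list; as printed, it is narrower and lacks I05.0x

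*Combined protocol and SAP*

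**What the plan says.** The trial criterion to be emulated is "Clinically significant (moderate or severe) mitral stenosis" (Appendix A, Exclusion 2). The claims version looks back 180 days and gives two code lines:

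- "ICD-9 diagnosis: 396.0x, 396.1x, 394, 746.5"
- "ICD-10 diagnosis: I34.2x, I05.1x, I05.2x"

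The Appendix A header adds a general note: "ICD-10 codes are not listed in this document because of excel cell size limitations and excessive number of ICD-10 codes". It continues: "Full ICD-10 code lists will be available in the above Google Drive Folder (link above". It also says how the lists were made: "ICD-9 to ICD-10 code conversions were completed using a SAS macro that implements forward/backward mapping".

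The flowchart in section 5.3 reports the patients removed at this step by database, but not by treatment or by ICD version. Section 5.2.1 lets patients enter from January 2013 to the end of 2017 (Medicare), 2018 (MarketScan) or 2019 (Optum).

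**The concern.** The cohort uses both coding systems, so each cohort-defining rule needs two lists that select the same patients. Here the ICD-9 list takes a whole category and the ICD-10 list takes part of one. Someone who implements the exclusion from the page would apply a wider rule in ICD-9 data than in ICD-10 data. If the missing code is the one that carries the named condition, the ICD-10 rule would keep patients whom the trial excluded.

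This matters in two ways. The emulated population would depart from the trial's on a stated exclusion. If the retained patients have a higher embolic risk and are unevenly spread between the arms, the hazard ratio would also shift. No mitral stenosis or valve covariate can be seen in the readable part of Table 1 (the table is cut off), so one cannot assume that matching would repair such an imbalance.

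**Working it through.** **1. The two printed lists side by side (Appendix A, Exclusion 2)**

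| ICD-9 entry | Printed ICD-10 entry |
|---|---|
| 394 (no decimal, so read as the whole category) | I05.1x and I05.2x only; I05.0x not printed |
| 396.0x, 396.1x | none evident |
| 746.5 | none evident |
| – | I34.2x |

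The absence of I05.0x and the whole-versus-part difference can be read directly from the page. Which ICD-10 code answers to which ICD-9 code depends on code titles, which the documents do not give. By the standard titles, to be confirmed from the sponsor's list, I05.0 is rheumatic mitral stenosis and I05.1 is insufficiency.

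**2. Does the header note explain the short ICD-10 line?** Only in part. It says ICD-10 codes are not listed, yet Exclusions 2, 4, 5, 6, 15, 17 and 18 print some. Exclusions 3, 13 and 14 print none, which is what reliance on the external folder looks like. The stated reason is cell size and number of codes, and a line of three codes is hardly at that limit.

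**3. Flowchart (section 5.3)**

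| Database | Before | Removed | After | Share removed |
|---|---|---|---|---|
| Optum | 120,711 | 320 | 120,391 | 0.27% |
| Truven (MarketScan) | 95,034 | 127 | 94,907 | 0.13% |
| Medicare | 543,154 | 626 | 542,528 | 0.12% |
| All | 758,899 | 1,073 | – | 0.14% |

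Each subtraction agrees with the printed remainder. The counts cannot show which codes produced them.

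**4. Size of a possible effect.** The documents give neither the missed share nor its event rate, so both are assumed. Let missed cases be a share *f* of the matched warfarin arm and none of the apixaban arm, with *m* times the event rate of the others. The warfarin rate is multiplied by (1 − *f*) + *f m* = 1 + *f*(*m* − 1), so

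observed HR = true HR / [1 + *f*(*m* − 1)].

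With a true HR of 0.79 (section 1.5):

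| *f* | *m* | Divisor | Observed HR |
|---|---|---|---|
| 0.25% | 2 | 1.0025 | 0.788 |
| 0.25% | 3 | 1.005 | 0.786 |
| 1% | 2 | 1.01 | 0.782 |
| 1% | 3 | 1.02 | 0.775 |
| 1% (stress case) | 5 | 1.04 | 0.760 |

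The range is generous. 0.25% to 1% is roughly 2 to 7 times the 0.14% removed by the whole step, and it means about 276 to 1,103 of the 110,259 matched warfarin patients.

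**5. Against the study's precision.** Section 10 expects 1,116 pooled events. With equal arms, SE(log HR) ≈ √(4/1,116) = 0.060. The shift at *f* = 1%, *m* = 3 is ln(1.02) = 0.020, a third of one SE.

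**6. Against the margin, with the direction reversed.** Put the same missed cases all in the apixaban arm. The HR is then multiplied by 1.02: 0.79 becomes 0.806, and 1.00 becomes 1.02. For the latter, the pooled upper 95% limit would be about exp(0.020 + 1.96 × 0.060) = 1.15, well below 1.38.

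**The case against.** The strongest reply is that the printed ICD-10 codes are not the operative ones. The header places the full lists elsewhere and says they were mapped from ICD-9, and it makes no exception for criteria that happen to print some ICD-10 codes. Partial printing occurs elsewhere too: the primary outcome prints an ICD-10 code for systemic embolism and none for stroke. This stands, to the extent that nobody can say from these documents that the exclusion as run failed. It does not remove the mismatch. If the folder list is complete, the printed line is wrong, in a document that section 12 plans to upload to the registry. If the folder list equals the printed line, the exclusion is wrong.

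A reader might go further and infer three things that the documents do not support:

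- **That ICD-10-coded cases were in fact missed.** The operative list is not available. Optum has the latest end date and the highest share removed, which does not suggest failure in later data. This is weak evidence, because the databases differ and the counts are not split by code version.
- **That missed patients are mainly warfarin users, so the HR is biased toward apixaban.** No section gives mitral stenosis by arm or says how such patients are treated. The pre-matching c-statistics of 0.901 to 0.911 (Appendix B) show strong treatment selection in general, but nothing about this condition.
- **That the bias grows because apixaban use falls in the later years.** This is so before matching. After matching, mean calendar day is 1,346.50 for warfarin and 1,295.54 for apixaban in Optum, and 850.64 and 831.37 in MarketScan. The Medicare row is not usable. Similar entry dates would not remove an imbalance within an era, but the supposed concentration is not seen where it can be checked.

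**Conclusion.** The point holds as a mismatch in a cohort-defining rule. As printed, the mitral stenosis exclusion would be narrower in ICD-10 data than in ICD-9 data. By the standard code titles, which need confirmation, it would leave out rheumatic mitral stenosis itself. Whether the exclusion as run has this gap is open until the operative list is seen.

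The likely numerical effect is small. Under the assumed inputs (0.25% to 1% missed in one arm only, two to three times the event rate), an HR of 0.79 moves to between 0.788 and 0.775 if the cases are in the warfarin arm. It moves the other way by a similar amount if they are in the apixaban arm. The documents do not show the direction. The non-inferiority conclusion against 1.38 is not at risk from this. The reason to act is fidelity to the trial's population and a registered specification that can be followed, not a material threat to the estimate.

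**What to change.** 1. Compare the printed ICD-10 line with the operative list in the external folder.
2. Make the ICD-10 list the full counterpart of the ICD-9 list: add I05.0x and the combined-valve and congenital counterparts, after confirming the titles.
3. Treat insufficiency-only codes the same way in both eras. Dropping I05.1x from ICD-10 while ICD-9 keeps all of 394 would only create a new mismatch.
4. Correct the appendix or the code, whichever is wrong, and say in the header note which printed ICD-10 lists are complete.
5. Rerun Exclusion 2, and the later flowchart steps and matching, if the operative list changes.
6. Report Exclusion 2 removals by arm and ICD version.

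The cost is one code-list check. If the operative list is already complete, only the text changes. If not, the cost is a rerun, with few patients likely to be affected, since the whole step now removes 0.14%.

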1.3.1 Required power for primary endpoint and noninferiority margin (if applicable)

The test was designed for noninferiority. For non-inferiority, the 95% CI should not include ≥ 1.38 to declare noninferiority and 99% CI should not include ≥ 1.44 to declare noninferiority. Assuming average follow-up period of 1.8 years and a stroke or systemic embolism rate of 1.67 per 100 subject-years, the power of the study will be 90% with 18,000 randomized patients and 448 patients with primary outcome.

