1.5 Trial estimate

HR = 0.79 (95% CI 0.66-0.95) comparing apixaban vs warfarin (Granger et al., 2011)

2. Person responsible for implementation of replication in Aetion

[name]., [name], MPH, and [name] implemented the study design in the Aetion Evidence Platform. They are not responsible for the validity of the design and analytic choices. All implementation steps are recorded, and the implementation history is archived in the platform.

[figure not shown]
3. Data Source(s)

United/Optum, MarketScan, Medicare

4. Study Design Diagram

The study design diagram visualizes key aspects of the longitudinal study design for expedited review.

Design Diagram – ARISTOTLE TRIAL REPLICATION

5. Cohort Identification

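### The prosthetic-valve exclusion prints procedure codes only for TAVR, so a recent surgical valve replacement not yet carrying a status code could enter the cohort

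*Combined protocol and SAP*

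**What the plan says.** Appendix A sets the trial's exclusion beside its claims implementation. The trial criterion is "Conditions other than atrial fibrillation that require chronic anticoagulation (e.g. prosthetic mechanical heart valve").

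The implementation has two parts:

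- Status diagnoses: "ICD-9 diagnosis: V43.3x ICD-10 diagnosis: Z95.2x". The stated window and setting are "Measured 180 days prior to and including day of drug initiation in any diagnosis position and inpatient or outpatient care setting".
- Procedures: a single list of 14 codes, "CPT procedure codes: (TAVR with prosthetic valve) 33361, 33362" and onward, with no other procedure group and no ICD procedure codes.

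The flowchart in Section 5.3 has one line for this step, "Excluded based on Exclusion #4 - Prosthetic heart valve". It gives counts by database but not by treatment arm or by type of code.

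The head of Appendix A explains why ICD-10 codes are not printed in full: "Full ICD-10 code lists will be available in the above Google Drive Folder (link above"). It also points to that folder, in general terms, for missing information.

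**The concern.** The criterion's own example is a mechanical valve, but the only procedure codes printed are labelled for catheter-implanted valves. A surgical replacement is caught only if somebody also recorded V43.3x or Z95.2x by the index day.

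The new-user design makes timing important. The 180-day washout (Sections 5.2 and 6.1) removes patients already on warfarin, including those with an older valve. The valve patients who could remain are therefore mainly those starting soon after surgery, when a status code has had least time to appear.

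Elsewhere Appendix A pairs status codes with procedures. Kidney transplant, for example, uses V42.0x together with ICD-9 procedure 55.6x.

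At stake is a small, possibly one-sided contamination of the warfarin arm. If the missed patients had more strokes and emboli, the primary HR would be too low. If they also bled more, the major-bleeding control (trial HR 0.69, Section 1.4) would shift in its expected direction and would not reveal the problem. No readable row of Table 1 names valve surgery as a covariate, although that table is cut.

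**Working it through.** **1. The plan's own figures.** Section 10, pooled: expected events = 2 × 110,259 × 5.06/1,000 = 1,115.82, as printed. With 1:1 allocation and two-sided alpha 0.05, power = Φ(√1,115.82/2 × |ln HR| − 1.96).
- HR 0.79: Φ(16.70 × 0.2357 − 1.96) = Φ(1.98) = 0.976, as printed.
- Margin 1.38: Φ(16.70 × 0.3221 − 1.96) = Φ(3.42) = 0.9997, as printed.

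The implied standard error of ln HR is √(4/1,115.82) = 0.060. It is used below as the yardstick.

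**2. What the exclusion caught (Section 5.3).** The subtractions are exact.
- Optum: 1,916/119,888 = 1.60%
- MarketScan (Truven): 1,004/94,598 = 1.06%
- Medicare: 8,562/540,705 = 1.58%
- Total: 11,482/755,191 = 1.52%

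These are patients found by the printed codes, both arms together. They do not measure how many were missed.

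**3. Size of a possible bias.** Let f be the excess share of missed valve patients in the matched warfarin arm, and k their event rate relative to other warfarin patients. Neither is in the documents; both are assumed. If none are on apixaban, the warfarin rate is multiplied by 1 + f(k − 1), so

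apparent HR = true HR / (1 + f(k − 1)).

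The true HR is set to the trial estimate in Section 1.5, "HR = 0.79 (95% CI 0.66-0.95) comparing apixaban vs warfarin".

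| f | k = 2 | k = 3 |
|---|---|---|
| 0.25% | 0.79/1.0025 = 0.7880 | 0.79/1.005 = 0.7861 |
| 0.5% | 0.79/1.005 = 0.7861 | 0.79/1.01 = 0.7822 |
| 1% | 0.79/1.01 = 0.7822 | 0.79/1.02 = 0.7745 |
| 2% | 0.79/1.02 = 0.7745 | 0.79/1.04 = 0.7596 |

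With k = 1 the HR does not move. In standard errors the shift runs from ln(1.0025)/0.060 = 0.04 to ln(1.04)/0.060 = 0.65.

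**4. Effect on the conclusions.** At f = 1% and k = 2 the two-sided type I error of the superiority test, at a true HR of 1, would rise from 0.050 to 0.053. For non-inferiority the rule is that "the 95% CI should not include ≥ 1.38 to declare noninferiority". The largest shift in the table, ln(1.04) = 0.039, is about 12% of ln(1.38) = 0.322.

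**5. An extreme case.** Suppose as many were missed as caught, all on warfarin: f = 11,482/370,862 = 3.1%, using the unmatched warfarin count in Appendix B. Then k = 3 gives 0.79/1.062 = 0.744, a shift of about one standard error. Nothing in the documents suggests a leak of this size.

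**The case against.** The case against a large effect is strong, and much of it stands.

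- **The status codes are a broad net.** They count in any position, inpatient or outpatient, up to and including the index day. Any surgical-valve patient with either code is already out.
- **Other rules narrow the leak.** AF entry needs a principal inpatient AF diagnosis within 7 days, or two AF diagnoses 14 to 351 days apart. A patient admitted for valve surgery with AF as a secondary diagnosis does not qualify by the first route. The exclusions for mitral stenosis and endocarditis remove some surgical candidates.
- **Matching may drop poorly overlapping patients.** Pre-match c-statistics are 0.901 to 0.911, and only 110,259 of 370,862 warfarin patients are matched. Matched hospitalizations (0.41 and 0.41) and hospital days (2.26 and 2.25) are balanced, so there is no visible sign of recent surgery in one arm. This does not prove absence.
- **The 2% upper assumption is high.** Even crediting all 11,482 caught patients to warfarin (3.1%), and taking matched and unmatched shares as similar, 2% missed would mean the exclusion fails for about 2/(2 + 3.1) = 39% of warfarin valve patients.
- **Printed lists can be incomplete.** The kidney-transplant CPT4 heading in Appendix A has nothing under it. However, the explanation for unprinted codes concerns ICD-10 only. It does not cover CPT or ICD-9 procedure codes, although the general pointer to the folder might.

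A reader might infer that valve-surgery patients enter freely, that essentially all of them are on warfarin, and that the HR is therefore biased toward apixaban. The documents do not support this. The flowchart is not split by arm, and no event rate for these patients is given.

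A reader might also point to the matched previous-cardiac-procedure row in Appendix B: 2,098 (1.9%) on warfarin against 1,126 (1.0%) on apixaban, having been 1.0% and 1.1% before matching. That row names CABG, PTCA and stent, not valves, and row labels in the extracted table may be displaced. It does not measure this leak.

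None of this supplies the missing surgical codes.

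**Conclusion.** The gap in the printed rule is real. Exclusion 4 names mechanical valves as its target, yet for surgical replacements it depends entirely on a status diagnosis being recorded in time. The consequence is conditional: a patient must have had recent surgery, lack both status codes through the index day, and pass the AF and washout rules.

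That such patients would mostly be on warfarin is a reasonable clinical inference, not a documented fact. A bias toward apixaban also needs a higher event risk. Under assumed shares of 0.25% to 2% and rate ratios of 2 to 3, a true 0.79 would read 0.788 to 0.760, so the effect runs from negligible to modest. If it exists it is systematic, and a larger sample would not remove it. The point merits correction before the comparative analysis because the repair is simple, not because a material bias has been shown.

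**What to change.** 1. Check the full code list behind Appendix A for surgical heart-valve replacement procedures. If they are already applied, print them under Exclusion 4; no cohort rerun is then needed.
2. If they are absent, add them (CPT, ICD-9-CM procedure and ICD-10-PCS) with the same 180-day window, before the Section 13 analyses, whose date is still blank.
3. Rerun cohort assembly, matching, balance (Section 9) and final power (Section 10).
4. Report Exclusion 4 removals by arm and by code type (status diagnosis, TAVR procedure, surgical procedure). This needs no outcome data. It would show how many extra patients the surgical codes catch and in which arm.

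The cost is one code list, a small loss of patients, and a repeat of the balance and power steps already reviewed on 9/8/20 and 9/29/20. A sensitivity analysis alone would test the concern at less cost, but would leave in the primary cohort any patients whom the trial criterion excludes.
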